The primary endpoint is an electroacoustic measurement of hearing aid function after a 90 day period of wearing the devices. The study may reveal that the product is robust and can

withstand adverse environments on human subjects. Conversely, it may reveal that the devices do not maintain their performance after being subjected to real-world, life situations. This may, in turn, delay development and/or launch of the intended product.

7 Inclusion and Exclusion Criteria

Inclusion criteria:

- N2, N3, or N4 sensorineural hearing loss
- Adult age 18 or older
- Participant must be willing to wear RIC devices in as many physically active environments as possible including showering and bathing

Exclusion criteria:

- Diagnosis that may cause fluctuations in hearing
- Unable to tolerate the physical fit of a RIC device coupled with standard silicone domes
- Inability to be seen for 3 lab visits

8 Measurements and procedures

Visit 1: (Day 1) 20 participants will be invited to the study based on their hearing loss experience. Researcher will obtain an updated audiogram, if last audiogram obtained is older than 1 year. Participants will be fitted with a pair of investigational devices and a charger case. They will be instructed on use and care of the hearing aids and charger case. Participants will be instructed to use them in a variety of specific environments including while showering/bathing, exercising, while in pool, golfing, etc. Electroacoustic evaluation will be conducted on the hearing aids at Test settings and at User Gain settings for baseline information. Participants will be provided questionnaires for the home trial.

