A device failure rate will be calculated as the percentage of all devices dispensed during the study which failed ANSI S3.22-2014 testing (on EIN) at the conclusion of the 90 day field trial. This value will be compared to the acceptance criterion of a 10% failure rate using a one sample binomial exact test. A p-value of less than 0.05 will indicate a statistically significant deviation in the sample from the acceptance criteria. **An observed failure rate significantly higher than 10% will indicate a failed acceptance criterion. An observed pass rate of 95% or higher will indicate a definitive pass acceptance criterion. In either of these cases, no statistical analysis will be necessary.**

Additional qualitative data will be collected regarding the participants' experiences, which will not be subjected to statistical analysis but will be summarized into key findings for the purpose of the study report.

10 Investigation Duration

The expected duration of each participant's participation is 90-100 days. The total expected duration of the clinical investigation is 15 weeks.

11 Data Handling and Management

Study data is recorded both with paper and with electronic Case Report Forms (p/eCRF). For each enrolled study participant a CRF is maintained. All CRFs are kept current to reflect the subject's status at each phase during the course of study. Participants cannot be identified in the CRF by name or initials and birth date but an appropriate coded identification is used. All study team members are authorized for the CRF entries and it is assured that any authorized person can be identified both for pCRFs and eCRFs. If pCRFs are used, the investigator's acronym as well as the subject ID is filled in and data are entered into an electronic file for analysis by the respective investigator and data get monitored by the assigned monitor. In case of a self-evident corrections, either the subject does it by himself or the investigator undertakes the correction by crossing out the word/sentence with a single horizontal line and by adding the correction including his personal identifier and the date.

Source documents for this investigation include, audiograms, Target fitting files, appointment checklists, and ANSI test measurement information and REM data.

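### Section 9 gives no verdict for 3 to 7 failures of 40 devices (3 to 8 if two-sided), including observed rates above the 10% limit; the recorded 100% pass rate is unaffected

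*Combined protocol and SAP*

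**What the plan says.** Section 9 defines a device failure rate with all dispensed devices as the denominator, a failure being an equivalent input noise result outside the data sheet value at the end of the 90-day trial. On the comparison it says: "This value will be compared to the acceptance criterion of a 10% failure rate using a one sample binomial exact test". On significance: "A p-value of less than 0.05 will indicate a statistically significant deviation in the sample from the acceptance criteria".

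The decision rule follows in three sentences:

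- Fail: "An observed failure rate significantly higher than 10% will indicate a failed acceptance criterion".
- Pass: "An observed pass rate of 95% or higher will indicate a definitive pass acceptance criterion".
- Waiver: "In either of these cases, no statistical analysis will be necessary".

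No sentence covers a pass rate below 95% whose failure rate is not significantly above 10%. The sidedness of the test is not stated: the significance sentence speaks of deviation, which suggests two-sided, while the fail sentence points upward only.

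Section 12 records that a justification for omitting the statistical analysis was added in version 2, the results having shown a 100% pass rate.

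**The concern.** The two verdicts use different kinds of threshold. Pass is a plain cut-off on the observed rate, set at 5% failures. Fail requires statistical significance against 10%, which in a small sample needs an observed rate well above 10%. Between them lies a band of counts with no stated conclusion, and the band straddles the 10% limit.

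Running the planned test does not close the band, because every count in it is non-significant and the plan gives non-significance no meaning. The conclusion would then be chosen after seeing the data. The easiest choice, that whatever has not failed is acceptable, would treat a lack of evidence against the product as evidence that it meets the limit.

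Section 4 calls the design confirmatory, Section 1 ties the study to acting on problems before launch, and Section 6 says a poor result may delay launch. A rule with that role should give an answer for every count.

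Separately, the waiver covers both verdicts. For the pass verdict that is coherent. For the fail verdict it is circular, since significance can be established only by the test being waived.

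**Working it through.** The documents give no critical count, power or sample-size calculation, so there is no stated figure to reproduce. The zones follow from the plan's own inputs.

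**Inputs**

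- Participants: "20 participants will be invited to the study based on their hearing loss experience" (Section 8, Visit 1). Enrolment is assumed equal to invitations.
- Devices: "Participants will be fitted with a pair of investigational devices and a charger case" (Section 8, Visit 1). So n = 20 × 2 = 40. This is derived; the documents do not state 40.
- Limit p₀ = 0.10 and significance level 0.05 (Section 9).

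**Pass zone.** (40 − x)/40 ≥ 0.95 gives x ≤ 2. Two failures are 5.0%; three are 7.5% and miss the threshold.

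**Fail zone.** The one-sided exact p-value is P(X ≥ x) = Σ C(40,k) 0.1^k 0.9^(40−k), summed over k = x to 40. The lower tail P(X ≤ x) shows whether a count is significantly below 10%.

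| Failures | Observed rate | Upper-tail p | Lower-tail p |
|---|---|---|---|
| 0 | 0% | 1.000 | 0.0148 |
| 1 | 2.5% | 0.985 | 0.0805 |
| 2 | 5.0% | 0.920 | 0.223 |
| 3 | 7.5% | 0.777 | 0.423 |
| 4 | 10.0% | 0.577 | 0.629 |
| 5 | 12.5% | 0.371 | 0.794 |
| 6 | 15.0% | 0.206 | 0.901 |
| 7 | 17.5% | 0.0995 | 0.958 |
| 8 | 20.0% | 0.0419 | 0.985 |
| 9 | 22.5% | 0.0155 | 0.995 |

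One-sided, failure starts at 8. Two-sided, 8 failures give p = 0.057 (minimum-likelihood method) or 0.084 (doubled tail), and 9 give 0.0155 or 0.031, so failure starts at 9. The unclassified counts are therefore 3 to 7 or 3 to 8. None of them is significantly below 10% either; only 0 failures is. At 7 of 40 the one-sided 95% exact upper limit is 30%.

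**How often the gap would be reached** (40 independent devices):

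| True failure rate | Pass (0–2) | No verdict, one-sided (3–7) | Fail, one-sided (≥8) | No verdict, two-sided (3–8) | 5–7 failures |
|---|---|---|---|---|---|
| 2% | 95.4% | 4.6% | <0.1% | 4.6% | 0.1% |
| 5% | 67.7% | 32.3% | 0.1% | 32.3% | 4.7% |
| 10% | 22.3% | 73.5% | 4.2% | 76.2% | 32.9% |
| 15% | 4.9% | 70.7% | 24.4% | 81.6% | 49.3% |
| 20% | 0.8% | 42.9% | 56.3% | 58.5% | 36.1% |

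**Sensitivity to n.** With 38 devices the gap is 2–7 (one-sided) or 2–8 (two-sided). With 36 it is 2–7 either way. With 20 it is 2–4, or 2–5 under doubled tails. It exists at each size.

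**The case against.** The strongest objection is that the outcome is already known. Section 12 records a 100% pass rate, which meets the pass rule whatever the number of devices, and rewording Section 9 now cannot restore prespecification. That stands. A reader might infer that the gap affected the launch conclusion; the documents do not support this.

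A second objection is that the rule implicitly classifies everything: calling 95% a definitive pass hints at passes of a lesser kind, and waiving analysis at the two ends suggests that the middle is tested. A reader might infer that anything not failed is accepted. Section 9 does not say so. The test cannot separate the counts in the middle, and that reading would accept 12.5% to 17.5% observed failures. A sponsor may choose a lenient burden of proof, but the choice has to be written down.

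A third objection is that the gap matters only for a poor product. This stands in part. At a true rate of 2% the gap is reached about one time in twenty, and at 20% the fail verdict is more likely than the gap under a one-sided test. Of the 73.5% at a true rate of 10%, 73.5 − 32.9 = 40.6 points are 3 or 4 failures, which do not exceed the limit.

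The circular waiver is mainly a wording slip, since nobody could declare significance without running the test. The likely intent was that no further analysis is needed. A reader might also infer from Section 12 that the whole rule was fitted to the result, but the log does not show which sentences of Section 9 date from version 2.

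Finally, 2 failures of 40 count as a definitive pass although the lower-tail p is 0.22, so the line between 2 and 3 is not a statistical one. That is correct, and the fix allows for it.

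**Conclusion.** The stated rule is incomplete. At 40 devices it gives no conclusion for 3 to 7 failures one-sided or 3 to 8 two-sided, and 5 to 7 of these (also 8 if two-sided) exceed the 10% limit. The gap is the most likely single outcome at true failure rates of 10% and 15%, and a minor one for a product at 2%. The waiver sentence is also inconsistent with the fail verdict.

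The zones rest on 40 devices, a derived figure, and on the plan's own test. The probabilities further assume independent devices; correlation within a participant's pair would change them but not the zones. The defect lies in the rule as written, is worth correcting at little cost, and has no bearing on the reported 100% pass.

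**What to change.** In Section 9:

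1. State whether the exact test is one-sided or two-sided.
2. Classify every count. Report a result that is neither a pass nor significantly above 10% as *acceptance not demonstrated*, with the exact confidence interval for the failure rate.
3. State that a non-significant test is not evidence of meeting the 10% limit.
4. Limit the no-analysis waiver to the pass verdict, and describe that verdict as an observed-rate threshold, not as statistical proof that the failure rate is below 10%.

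This needs wording only, with no new data or participants. As results are already recorded, it should be entered as a dated clarification, and its practical value lies in the study report and in any reuse of the rule. The downside is that some intermediate results could no longer be presented as acceptable.

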Visit 2: (Day 45) Participants will be asked if they have experienced any issues with hearing performance or sound quality (including feedback or gain changes) during the home trial. Participants will be asked to identify their charging behavior, including the number of charges from the onboard battery alone. Participants will be asked to provide any additional feedback regarding the hearing aids and charger case. Participants will be asked to rate the ease of use of the hearing aids and charger case. Participants will be asked to rate their comfort level wearing the hearing aids during the requested activities. They will be asked to rate their overall satisfaction with the hearing aids, charger case, and the combined system so far. If the participant requests any fine-tuning or adjustment to the hearing aid settings, they can do so at this time. . Electroacoustic evaluation will be conducted on the hearing aids at Test Settings and compared to the baseline testing.

Visit 3 (Day 90): Participants will come to the clinic to return the hearing aids and charger case. Datalogging information will be downloaded from the hearing aids to verify wearing times. Participants will be asked the same questions as on Visit 2. Electroacoustic evaluation will be conducted on the hearing aids at Test Settings and User Gain settings and compared to the baseline testing.

9 Statistical design and analysis plan

All subjects are exposed to the same treatment for the same total duration. As such, all subjects will be treated as a single cohort for analysis. The primary endpoint will be defined as a binary variable indicating whether the device performance has degraded as defined by comparing electroacoustic analysis (per ANSI S3.22-2014). Indicator of performance degradation in this investigation is: equivalent input noise (EIN) beyond the value specified on the product data sheet. All devices will be confirmed to comply with the data sheet prior to being dis-

pensed in the study. Devices which fail testing at the conclusion of the study will be recorded as a failure.

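### Section 9 calls an observed pass rate of 95% or more 'definitive' and waives the analysis, although at 40 devices 1 or 2 failures meet that rule without excluding the plan's own 10% limit

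*Combined protocol and SAP*

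**What the plan says.** Section 4 describes the design as confirmatory. Section 9 defines the device failure rate as the "percentage of all devices dispensed during the study which failed" the electroacoustic test (on equivalent input noise) at the end of the field trial. It names the analysis: "This value will be compared to the acceptance criterion of a 10% failure rate using a one sample binomial exact test", with p below 0.05 as the mark of significance. The sidedness of the test is not stated.

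Two decision clauses and a waiver follow:

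- Fail: "An observed failure rate significantly higher than 10% will indicate a failed acceptance criterion".
- Pass: "An observed pass rate of 95% or higher will indicate a definitive pass acceptance criterion".
- Waiver: "In either of these cases, no statistical analysis will be necessary".

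On numbers, section 8 says "20 participants will be invited to the study based on their hearing loss experience" and "Participants will be fitted with a pair of investigational devices and a charger case". Section 12 records that a justification for doing no statistical analysis was added in version 2, because every device had passed.

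**The concern.** The plan has a stated limit and a named test against it. At the point where the favourable conclusion is drawn, it replaces that test with a cut-off on the observed rate. An observed rate of 95% or more does not by itself show that the true failure rate is below 10%; that depends on how many devices were tested. In a study called confirmatory, a reader will take 'definitive' to mean that the limit has been excluded. Under the printed rule the label could be given to data that do not exclude it, with no test or interval required to reveal this.

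Two smaller points of drafting sit in the same paragraph. The fail clause depends on significance, which can be known only from the test that the waiver removes. And the failure rate has a stated denominator (devices dispensed) while the pass rate has none, so the two need not add to 100% if a device goes untested.

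**Working it through.** **Inputs**

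- Limit p0 = 0.10, exact binomial test, 0.05 level: section 9. Sidedness is not given, so both are shown.
- Pass threshold 95%: section 9.
- Devices: 20 participants × 2 = 40, derived from section 8. This assumes that all those invited are fitted and that no extra devices are dispensed.
- Devices are treated as independent, as the one-sample test does.

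The document gives no power, p-value or confidence limit, so there is no figure of the plan's own to reproduce.

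**Which counts qualify.** 38/40 = 95.0% meets the threshold; 37/40 = 92.5% does not. So 0, 1 or 2 failures qualify.

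**Lower-tail exact p, P(X ≤ x) with n = 40 and p0 = 0.10**

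- x = 0: 0.9^40 = 0.0148
- x = 1: 0.0148 + 40 × 0.1 × 0.9^39 = 0.0148 + 0.0657 = 0.0805
- x = 2: 0.0805 + 780 × 0.1^2 × 0.9^38 = 0.0805 + 0.1423 = 0.2228

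**Upper limit (Clopper-Pearson).** This is the p at which P(X ≤ x) equals 0.05 (one-sided 95%) or 0.025 (two-sided 95%). For x = 0 it is 1 − 0.05^(1/40) = 7.2%, or 1 − 0.025^(1/40) = 8.8%.

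| Failures of 40 | Observed pass rate | Lower-tail p | Two-sided p | One-sided upper limit | Two-sided upper limit | Excludes 10%? |
|---|---|---|---|---|---|---|
| 0 | 100% | 0.015 | 0.030 | 7.2% | 8.8% | yes |
| 1 | 97.5% | 0.080 | 0.180 | 11.3% | 13.2% | no |
| 2 | 95.0% | 0.223 | 0.429 | 14.9% | 16.9% | no |

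The last column is the same for either sidedness.

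**Chance of the label, P(X ≤ 2) at n = 40.** 22.3% at a true failure rate of 10%, 10.8% at 12.5%, 4.9% at 15% and 0.8% at 20%. The first figure is 0.2228 / 0.05 = 4.5 times the plan's significance level.

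**If fewer than 40 devices are tested.** With 38, 36 or 30 devices, one failure still qualifies (37/38 = 97.4%, 35/36 = 97.2%, 29/30 = 96.7%) and still does not exclude 10% (lower-tail p = 0.095, 0.113, 0.184). The finding does not depend on exactly 40.

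**The recorded result.** With no failures, the one-sided test excludes 10% when 0.9^n < 0.05. Since 0.9^28 = 0.052 and 0.9^29 = 0.047, at least 29 tested devices are needed. At 40 the condition is met comfortably.

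**The case against.** The strongest reply is that a cut-off on the observed rate is a legitimate acceptance rule. The 95% threshold is already stricter than the 90% pass rate that the limit implies, and the printed test asks only whether failures are significantly above 10%, not whether 10% is excluded from below. The waiver is also not total: results between the two clauses still go to the exact test. Every device passed, so the weak part of the rule was never used. And the public text may be a condensed one, since section 12 cites section numbers that do not appear here.

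Much of this stands. It limits the consequence, and it makes the circular fail clause a slip of wording, because significance plainly refers to the test named just before. It does not rescue the word 'definitive': a point-estimate rule is acceptable if it is labelled as one and its error rates are given, and the printed text does neither.

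A reader might be tempted to go further in three ways that the document does not support:

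- *That the 100% pass is unsupported.* Zero failures in 40 independent devices excludes 10%.
- *That the 95% rule was written after the result.* Section 12 says that the justification for omitting the analysis was added then; it does not say that the threshold was.
- *That untested devices would be counted as passes.* Section 9 says "Devices which fail testing at the conclusion of the study will be recorded as a failure" and counts failures over devices dispensed, but it does not define the pass rate, so this cannot be inferred. No unreturned or untested device is recorded.

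**Conclusion.** The concern holds against the rule as printed. At 40 independent devices, two of the three counts that earn 'definitive pass' do not exclude the 10% limit (one-sided upper limits 11.3% and 14.9%), and a device exactly at the limit would earn the label 22.3% of the time.

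It is a minor point, because the recorded outcome probably stands. That rests on two assumptions: that about 40 devices were tested, which the document does not state, and that the two devices of a pair fail independently. In the extreme case where pairs always fail together, the information is 0/20, and the one-sided upper limit is 1 − 0.05^(1/20) = 13.9%. The document gives no estimate of that dependence. What remains for this study is reporting: the document gives the 100% pass without the number tested or a limit. The internal study report named in section 19 was not available and may give both.

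**What to change.** In section 9:

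(a) Delete the sentence "In either of these cases, no statistical analysis will be necessary".

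(b) In every case report devices dispensed, tested and failed, with the exact binomial test against 10% and the matching exact limit. State one sidedness and use it for both. The one-sided lower-tail test at 0.05 and the one-sided 95% Clopper-Pearson upper limit always agree. Two-sided versions can conflict: 0/35 gives an exact p of 0.045 but an upper limit of 10.003%.

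(c) Reserve 'definitive pass' for results whose upper limit is below 10% (0 failures at 40 devices). Report any other result of 95% or more as 'observed rate within the acceptance criterion', with its limit.

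(d) Calculate both the failure rate and the pass rate on devices tested, and list untested devices separately.

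(e) State as a limitation that paired devices are analysed as independent.

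For the completed study, report 0/n with its exact limit (if n = 40: p = 0.015, one-sided upper limit 7.2%), and do not present the revised rule as pre-specified.

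The cost is wording plus one calculation on data already collected. No device newly fails, because a result of 95% or more keeps a favourable label. The downside is that 'definitive' becomes harder to earn at 40 devices: with a true failure rate of 2%, the chance is 0.98^40 = 45%, against P(X ≤ 2) = 95% under the present rule.
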